### 9.1.1 Retrospective Cohort Design

A retrospective cohort of exposed subjects will be selected. Subjects will enter the exposed cohort upon their first vaccination with AZD1222. Subjects in the AZD1222 cohort will be matched, as applicable, to 3 different comparator cohorts: concurrent unvaccinated subjects, active comparators (ie, subjects vaccinated with an mRNA vaccine against COVID-19), and historical comparators enrolled in the study data sources during the pre-pandemic period (ie, from 2017 to 2018). The AZD1222 cohort will be matched, as applicable, independently to the 3 different comparator cohorts on calendar date of vaccination, age, sex, region, prior COVID-19, and status according to each of the 5 special populations (Section 9.2.1.2). Propensity scores (PSs) will be used to address confounding, balancing multiple covariates such as comorbidities, markers of healthcare utilisation and comedication between the vaccinated and the different comparator cohorts (Austin 2014, Webster-Clark et al 2021). Relative risk will be the main measure of effect, which will be estimated using incidence rate ratios (IRRs), prevalence proportion ratios (PPRs), or hazard ratios (HRs), depending on the analysis and outcome. Absolute risk difference measures will include incidence rate differences, prevalence proportion differences (PPD), and  $1 - KM^2$  differences.

In the cohort study, the initial plan was to use concurrent, rather than historical, comparator (unvaccinated) subjects because they are at risk for COVID-19, and COVID-19 may function as an important covariable in the analyses of several of the safety endpoints. Moreover, both healthcare-seeking behaviours and healthcare delivery during the pandemic differ from those during the pre-pandemic era. The potential challenge with this approach is that during the pandemic, concurrent unvaccinated subjects in the comparator group may themselves become vaccinated over time. Results from Interim Reports 1 and 2 confirmed that the duration of follow-up among concurrent unvaccinated subjects was short (median, < 2 months in all data sources) and probably not long enough to evaluate AESIs with unknown risk window—(those with a risk window that ends at 180 or 365 days). Thus, additional comparators for whom the follow-up is expected to be longer were requested by the PRAC and have been added to the

---

[figure not shown]
 KM, Kaplan-Meier estimate.

protocol. These include historical comparators from the pre-pandemic era and active comparators. This study will select historical comparators from the pre-pandemic era (2017-2018) matched by age, sex, region, and the first vaccination date of the exposed subjects minus 3 or 4 years—an approach that could control for seasonality. Concerns about non-comparability remain as the background rate of AESIs may have changed during the pandemic due to the effects of COVID-19 or because of less intensive ascertainment due to access issues or healthcare-seeking behaviours. Additionally, this study will select active comparators (subjects vaccinated with mRNA vaccines, either Comirnaty or Spikevax) matched by age, sex, prior COVID-19, region, and the first vaccination date. The inclusion of active comparators is also challenging due to lack of overlapping age distribution between AZD1222 subjects and subjects vaccinated with mRNA vaccines observed in Interim Report 2. A pre-matching feasibility assessment of cohort comparability will be performed to examine the overlap of matching covariates before matching in the AZD1222 cohort and the active comparator cohort. This will henceforth be referred to as the feasibility assessment of cohort comparability. Section 9.7.3.4 details the content of the feasibility assessment of cohort comparability, the results of which will guide and inform the suitability of the active comparator cohort analysis.

### 9.1.2 Self-controlled Risk Interval Design

A complementary approach for Primary Objectives 3 and 4, an SCRI analysis, will be used to assess relative risks for AESIs meeting the criteria for this specific design (ie, acute onset, short latency, risk intervals that are relatively well known, that the occurrence of the event must not affect the probability of vaccination, and that the occurrence of the event of interest must not censor or affect the observation period) (Weldeselassie et al 2011). The SCRI is a case-only study that includes only individuals who were vaccinated with AZD1222 who experienced an outcome during the study period (Tokars et al 2012). The IRR comparing the IR of the AESI(s) in a period hypothesised to be at increased risk due to exposure (“risk period” or “exposed person-time”) will be compared with a prespecified postvaccination period within the same individual that falls after the risk period (“control period” or “unexposed person-time”). Limiting the selection of control periods to after vaccination will minimise the potential biases of other self-controlled designs that include comparator time before vaccination and require the assumption that prevaccination events do not affect the probability of subsequent vaccination (Weldeselassie et al 2011). Figure 1 illustrates the design of the SCRI analysis.

**Figure 1 Self-controlled Risk Interval Design**

Note: Example with a risk period of 42 days and a control period of 42 days.

ACCESS, vACCine Covid-19 monitoring readinESS; COVID-19, coronavirus disease 2019; T, time measured in days.

Source: “Safety evaluation of COVID-19 vaccines in electronic healthcare databases: a protocol template from the ACCESS project.”

The cohort study is proposed as the primary approach because, unlike the SCRI design, this approach can be used to study outcomes with gradual onset (eg, multiple sclerosis), long latency, and/or risk intervals that cannot be well defined (eg, chronic fatigue syndrome), and it also allows estimation of risk difference. On the other hand, the main strengths of the SCRI design are that it implicitly adjusts for time-invariant confounders and that it can still be used to estimate relative risk even if everyone is vaccinated during the study period. Moreover, in contrast to the cohort design, including only exposed individuals minimises exposure misclassification due to imperfect capture of vaccinations in secondary data sources.

## 9.2 Setting

### 9.2.1 Population

The source population for each of the study designs will comprise all individuals registered in each healthcare data source (Section 9.4) during the study period.

#### 9.2.1.1 Cohort Design: Study Population

##### 9.2.1.1.1 ALL AZD1222 VACCINATED POPULATION

The *all AZD1222 vaccinated population* will include all subjects vaccinated with at least 1 dose of AZD1222 during the study period. No other inclusion or exclusion criteria will be applied. For each AESI, subjects who had an event of a specific AESI (Table 3) during the clean look-back interval were excluded from the cohort included in the analysis for the specific AESI with which they had history, but not from the analysis cohorts for other AESIs.

The **index date** will be the date when a subject received the first AZD1222 dose within the study period. Subjects who received AZD1222 after another COVID-19 vaccine as a second or third dose only will also be included in this population.

This population will be included in the analysis to address primary objective 4 and secondary objective 4 of the study (SCRI design).

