### Inclusion Criteria

#### AZD1222 Matched Cohort

Subjects in the **AZD1222 matched cohort** will include those subjects in the *all vaccinated first dose population* (ie, received at least 1 dose of AZD1222 within the study period, and this was their first COVID-19 vaccine dose) that fulfil *all* the following inclusion criteria:

- Have at least 12 months of data available before the index date
- Have no record of vaccination with any other COVID-19 vaccine on or before the index date

The **index date** will be the date when a subject receives the first AZD1222 dose within the study period.

For the comparison with the active comparator cohort, only AZD1222 vaccinees with a first and second dose of AZD1222 will be selected. The **index date** for this comparison will be the date of the second dose.

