### 9.2.1.3 SCRI Design: Study Population

For each outcome of interest to be evaluated using the SCRI design, the eligible population will include subjects from the AZD1222 cohort who experienced the outcome of interest during the study period. Only selected outcomes with well-characterised risk intervals will be evaluated using this approach (Section 9.3.2). Consistent with other vaccine studies that have used this approach ([Lee et al 2011](#)), events of interest must not have occurred in the recent past in order to distinguish between ongoing care for a historical event and an incident or recurrent event. Accordingly, each outcome will require a “clean” (ie, event-free) interval before the start of observation, which will vary by outcome; proposed specifications for this “clean look-back interval” appear in [Table 3](#). Specific criteria for selection of individuals for the SCRI design will require that:

- The subject received at least one dose of AZD1222
- The subject experienced the event during the risk or control interval
- There is at least 1 day of data accrual, which is used to define the event in the risk and control intervals combined, taking into account the data lag and timing of data extraction.

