#### 9.7.5 Missing Data

Because the underlying data represent attended medical care, we generally assume that the absence of information of clinical events or prescriptions/dispensings indicates an absence of the condition or the treatment. Therefore, no missing data on diagnosis and medications are expected.

Missingness is only expected for some lifestyle or biometric data, such as smoking status or BMI in primary care electronic medical records. In the other data sources, these variables are not captured and will be defined based on proxies that do not have missing data (ie, use of smoking cessation drugs or diagnosis of obesity). In the main analysis, when describing a variable, subjects with missing values will be reported as a separate category.

The presence of missingness will be analysed. In the case of < 10% of missingness, a complete-case analysis is proposed for the main analysis. A complete-case analysis consists of performing the adjusted analyses described in the next subsections only among subjects with no missing values, under the assumption that data are missing completely at random. However, in the case of > 10% of missingness for key covariates, multiple imputation will be explored.

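### The SCRI population needs no data before vaccination, so the 180- to 365-day clean look-back in Table 3 can be passed without being observed

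*Protocol*

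**What the plan says.** Protocol section 9.2.1.1.1 defines the all AZD1222 vaccinated population by at least one AZD1222 dose in the study period, then states "No other inclusion or exclusion criteria will be applied". On history it says only that "subjects who had an event of a specific AESI (Table 3) during the clean look-back interval were excluded from the cohort". It gives the population this use: "This population will be included in the analysis to address primary objective 4 and secondary objective 4 of the study (SCRI design". The source population in section 9.2.1 is "all individuals registered in each healthcare data source (Section 9.4) during the study period", with no minimum time registered.

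Section 9.2.1.3 gives the reason for a clean interval: "events of interest must not have occurred in the recent past in order to distinguish between ongoing care for a historical event". The aim is to tell such care apart from a new or returning event. Each outcome needs an event-free "interval before the start of observation, which will vary by outcome". The three selection criteria that follow are a dose, an event in the risk or control interval, and at least one day of accrual in those two intervals combined. Both intervals lie after vaccination.

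Footnote k of Table 3 describes the clean interval as a look-back in which no event was observed. It does not say that the interval must be covered by data.

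In section 9.2.1.1.3 the AZD1222 matched cohort must "Have at least 12 months of data available before the index date". The concurrent unvaccinated, active and historical comparators have the same 12-month requirement.

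**The concern.** A clean look-back separates new from old events only if the person was under observation during it. For someone who joined the data source shortly before vaccination, an empty look-back mostly reflects missing history. If an older condition is then coded in the weeks after vaccination, the stated rules count it as a new event.

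The self-controlled comparison does not remove this by itself. Section 9.1.2 claims adjustment for time-invariant confounders, whereas the recording of old disease after registration can vary over time within a person. The control interval always follows the risk interval, so any time pattern in that recording is confounded with the exposure contrast.

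The SCRI matters here. It serves primary and secondary objective 4. Section 9.9.1 relies on it against residual confounding and names it as the fallback if comparable unvaccinated subjects become scarce.

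**Working it through.** The protocol gives no figure for this point, so there is none to reproduce. The check has three parts.

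**1. Do the rules require an observed look-back?**

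| Rule | Matched cohorts | SCRI |
|---|---|---|
| Data before index | 12 months (9.2.1.1.3) | none (9.2.1.1.1, 9.2.1.3) |
| Data after vaccination | – | at least 1 day in the risk and control intervals combined |
| History exclusion | event in look-back | event in look-back |
| Meaning of clean | no event observed (Table 3, footnote k) | the same |

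Table 3 marks 16 events as SCRI-suitable. The look-back is 365 days for 14 of them, 183 for encephalitis and 180 for anaphylaxis. A subject with 21 days of prior data would leave 365 − 21 = 344 days of a 365-day look-back unobserved (94%) and still qualify.

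**2. How many vaccinees could be affected?** The protocol gives no count with short history. The only related figures are the Interim Report 2 counts in Table 4.

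- Vaccinated: 4,301,194 + 530,226 + 614,472 + 343,478 + 175,149 = 5,964,519.
- Matched: 3,938,490 + 517,015 + 609,842 + 336,889 + 154,858 = 5,557,094.
- Gap: 407,425, and 407,425 / 5,964,519 = 6.8%.
- By source: CPRD 362,704 / 4,301,194 = 8.4%; PHARMO 20,291 / 175,149 = 11.6%.

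This caps the share with under 12 months of data only if the vaccinated count was taken before the 12-month rule. It also includes subjects unmatched for any other reason.

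**3. What could it do to the estimate?** Take equal risk and control intervals. Let f be the share of SCRI cases that are old disease and q the share of those recorded in the risk interval. The expected share of cases in the risk interval is

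a = (1 − f) × IRR / (1 + IRR) + f × q, and the observed IRR = a / (1 − a).

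Example with f = 5%, q = 1 and true IRR 1: a = 0.95 × 0.5 + 0.05 = 0.525, and 0.525 / 0.475 = 1.11. Both f and q are assumptions.

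| True IRR | q | f = 2% | f = 5% | f = 10% |
|---|---|---|---|---|
| 1 | 1 (all in risk interval) | 1.04 | 1.11 | 1.22 |
| 1 | 0.5 (even) | 1.00 | 1.00 | 1.00 |
| 1 | 0 (all in control interval) | 0.96 | 0.90 | 0.82 |
| 2 | 0.5 (even) | 1.97 | 1.93 | 1.86 |

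Early recording raises the ratio. Even recording leaves a null unchanged but pulls a true excess towards 1. Late recording lowers the ratio.

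**The case against.** The other side has five arguments.

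- **Implied observation.** An event-free interval could be read as one that was observed. Footnote k does not support that, since it asks only that no event was observed. Section 9.7.5 points the same way, because "absence of information of clinical events or prescriptions/dispensings indicates an absence of the condition". That section concerns missing data in general and does not address time before registration, so the point does not rest on it.
- **Which population.** Section 9.2.1.3 draws SCRI subjects from the AZD1222 cohort, which could mean the matched cohort with its 12-month rule. Section 9.2.1.1.1, however, names the unrestricted population for the SCRI. The two wordings should be aligned in any case.
- **Left to the SAP.** Annex Table 1 lists the duration of available look-back among the variables that define the cohorts and leaves definitions to the SAP. Section 9.2.3.2 defers risk intervals and washouts. Neither states a prior-data criterion, while the protocol expressly closes the list of criteria for this population.
- **Limited weight.** The SCRI is complementary and the cohort is primary. SCRI outcomes are meant to be acute, and intervals after dose 2 lie further from registration. This stands, and it limits the likely effect.
- **Direction and size.** A reader might infer that old disease loads onto the risk interval and so creates a false vaccine signal. The documents say nothing about when old conditions are recorded. ARS Toscana, for example, is described through admissions, dispensings and registries rather than entries made when a patient joins a practice. A reader might also apply the full 6.8%. With assumed rate multipliers of 5 in the risk interval and 3 in the control interval, that gives (0.932 + 0.068 × 5) / (0.932 + 0.068 × 3) = 1.12. If the 6.8% had registered evenly over the year and only the last month mattered (6.8% / 12 = 0.57%), the same multipliers give (0.9943 + 0.0057 × 5) / (0.9943 + 0.0057 × 3) = 1.01. With the last three months (1.7%) they give 1.03. None of these is an estimate of the actual bias.

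**Conclusion.** The point holds as a badly fixed eligibility rule. As written, the SCRI admits subjects whose clean look-back is largely unobserved. This defeats the purpose that section 9.2.1.3 gives for the look-back and departs from the 12-month rule used for every matched cohort.

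It does not hold as a claim of upward bias or of a particular magnitude. In the illustration, with 2% to 10% of cases being old disease, a true ratio of 1 could appear as 0.82 to 1.22, and a true ratio of 2 would fall to between 1.97 and 1.86 under even recording. These ranges rest on assumed f and q. The 6.8% from Table 4 is a loose ceiling on the share of vaccinees with under 12 months of data. It is not the share of SCRI cases that are old disease. The change is worth making because it is cheap and the effect cannot be bounded from the protocol.

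**What to change.** In section 9.2.1.3, and in 9.2.1.1.1 for SCRI use, state that subjects must have data covering at least the event-specific clean look-back in Table 3 before the first AZD1222 dose. The 12 months already used for the cohorts would be simpler. It is longer than needed for anaphylaxis (180 days) and encephalitis (183 days), so it would drop some subjects whose required look-back is fully observed. Reword footnote k so that clean means observed and event-free, and use one population name in both sections. Report the number excluded by data source.

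The cost is one inclusion line and a filter of the kind the cohorts already need. The loss is at most about 7% of vaccinees if the Table 4 gap is taken as a ceiling (8.4% in CPRD, 11.6% in PHARMO). The loss of SCRI cases may differ somewhat from that. Table 1 schedules the revised SCRI inclusion criteria for the final report analyses, so the change can be made alongside them.

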#### 9.2.1.1.2 ALL AZD1222 VACCINATED FIRST DOSE POPULATION

Among all subjects in the *all AZD1222 vaccinated population*, only those subjects that received AZD1222 as their first COVID-19 vaccine dose (subjects who received AZD1222 as their second or third, but not as first, COVID-19 vaccine dose will be excluded) will be included in the *all AZD1222 vaccinated first dose population*. To ensure a minimum quality of the data, subjects with missing values for age and sex will be excluded. This population will be included in the analysis to address primary objective 2 and secondary objective 2 (patterns of use). The **index date** will be the date when a subject received the first AZD1222 dose as their first COVID-19 vaccine dose ever.

An *all mRNA vaccinated first dose population* will also be generated in order to describe the patterns of use of the vaccines included in the active comparator cohort. This will include subjects who received at least 1 dose of an mRNA vaccine (Comirnaty or Spikevax) during the study period and for whom that dose was their first COVID-19 vaccine dose (subjects who received an mRNA vaccine as their second or third COVID-19 vaccine dose after a first dose with a vaccine other than mRNA will be excluded). Subjects with missing values for age and sex will be excluded. The **index date** will be the date when a subject received the first mRNA dose as their first COVID-19 vaccine dose ever.

#### 9.2.1.1.3 MATCHED POPULATIONS

Subjects in the *all AZD1222 vaccinated first dose population* fulfilling eligibility criteria will be matched to 3 different comparator cohorts. Three independent sets of matched populations will be constructed: AZD1222 concurrent unvaccinated comparators; AZD1222 active comparators in the *all mRNA vaccinated first dose population*; and AZD1222 historical comparators. Each of these 3 sets of matched populations will be used to address primary and secondary objectives 1, 3 and 4. [Figure 2](#), located at the end of this section (after the descriptions of the cohorts), illustrates the assembly of the study cohorts.

### Inclusion Criteria

#### AZD1222 Matched Cohort

Subjects in the **AZD1222 matched cohort** will include those subjects in the *all vaccinated first dose population* (ie, received at least 1 dose of AZD1222 within the study period, and this was their first COVID-19 vaccine dose) that fulfil *all* the following inclusion criteria:

- Have at least 12 months of data available before the index date
- Have no record of vaccination with any other COVID-19 vaccine on or before the index date

The **index date** will be the date when a subject receives the first AZD1222 dose within the study period.

For the comparison with the active comparator cohort, only AZD1222 vaccinees with a first and second dose of AZD1222 will be selected. The **index date** for this comparison will be the date of the second dose.

#### Concurrent Unvaccinated Comparators Cohort

A potential comparator subject (**concurrent unvaccinated comparators**) will be eligible to be matched from the date the subject meets *all* the following inclusion criteria:

- Has at least 12 months of prior data available.
- Has not received any COVID-19 vaccine, including AZD1222.

The **index date** for the unvaccinated subjects will be assigned as the index date of the matched vaccinated subject.

Unexposed subjects that are eligible at the index date of an exposed subject with the same age ( $\pm 2$  years), sex, prior diagnosis of COVID-19, and status according the 5 special populations will be **matched** to the exposed subject. Matching will be done with replacement in a ratio of 1 vaccinated to 1 unvaccinated subject.

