### Historical Comparators Cohort

A potential comparator subject (**historical comparators**) identified during the period between 2017 and 2018 will be eligible to be matched from the date the subject met all the following inclusion criteria:

- Had at least 12 months of prior data available.

The **index date** for the historical comparators will be same day and month of the AZD1222 index date minus 3 years (subjects from 2018) or 4 years (subjects from 2017)—an approach that intends to address seasonality.

Subjects will be **matched** to AZD1222-vaccinated subjects on age ( $\pm 2$  years), sex, region, and status according to the 5 special populations. Matching will be done with replacement at a ratio of 1:1.

Whether all potential comparators, or only a sample, will be included in the selection of the comparator cohorts will depend on the data governance rules and data management capabilities of each research partner, which is still to be determined. The SAP will document this decision, along with other details about matching criteria.

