### Exclusion Criteria

The following exclusion criterion will be considered in all the cohorts:

[figure not shown]
- For each AESI, subjects (in any matched cohort) who had a specific AESI (Table 3) during the look-back period before the index date will be excluded from the cohort for the analysis of that specific AESI, but not from the cohorts for analysis of other AESIs.
  - If a subject had a specific AESI between the index date and the start of the risk window or had any censoring criteria within this time period, the subject will be excluded from the analysis of that specific AESI.

The number of subjects in the *all AZD1222 vaccinated first dose population* and in the *all mRNA vaccinated first dose population* excluded because they had no matches will be described. Similarly, the number of subjects in the initial pool of potential concurrent

unvaccinated comparators and historical comparators that fulfil the inclusion criteria but are excluded because they had no matches will be described.

In the analysis of a specific AESI, if a subject in the *AZD1222 matched cohort* is excluded due to having a prior history of that specific AESI, all its matched subjects will also be excluded from that analysis. Analogously, if the matched subject in the *concurrent unvaccinated comparator* matched cohort or in the *active comparator* matched cohort or in the *historical comparator* matched cohort is excluded, then the corresponding subject in the *AZD1222 matched cohort* will also be excluded from the analysis of that specific AESI.

**Figure 2** Assembly of Study Cohorts

[figure not shown]

Note: The process illustrated here will be conducted separately in each data source. Index date refers to the date of the first dose of AZD1222 for each vaccinee and for each unvaccinated comparator subject (minus 3 or 4 years for each matched historical control) or the date of the first dose of an mRNA vaccine for each active comparator subject. Subjects in the concurrent unvaccinated cohort will be allowed to enter the AZD1222 or the active comparator cohort if they later fulfil specific cohort entry criteria.

Note that the comparative analysis between AZD1222 and active comparator cohorts will be conducted among vaccinees who have received 2 doses. COVID-19, coronavirus disease 2019; SCRI, self-controlled risk interval.

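### No eligibility rule requires a concurrent or historical comparator to be out of hospital, or still present in the data source, on the assigned index date

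*Protocol*

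**What the plan says.** Section 9.2.1 starts from the widest base: "The source population for each of the study designs will comprise all individuals registered in each healthcare data source". Section 9.2.1.1.3 then sets two inclusion criteria for a concurrent unvaccinated comparator, "Has at least 12 months of prior data available" and "Has not received any COVID-19 vaccine, including AZD1222". For a historical comparator there is one: "Had at least 12 months of prior data available".

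The concurrent comparator's index date "will be assigned as the index date of the matched vaccinated subject", and the historical comparator takes the vaccinee's day and month moved back 3 or 4 years. No encounter of the comparator's own anchors the date. Matching is on age, sex, special-population status and region (region for the concurrent cohort comes from 9.1.1), plus prior COVID-19 for the concurrent cohort.

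The exclusions open with "The following exclusion criterion will be considered in all the cohorts" and are AESI-specific: the same AESI in the look-back, or the AESI or a censoring event before the risk window opens.

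Under 9.2.3.1, someone who leaves the area is censored only when enrolment formally ends. Until then 9.7.5 assumes that "absence of information of clinical events or prescriptions/dispensings indicates an absence of the condition or the treatment".

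**The concern.** Being vaccinated on a given day is evidence of being there and well enough to attend. The comparator side has no equivalent condition, and two groups can enter with few or no vaccinee counterparts.

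- **Inpatients.** People in hospital for another reason on the index date may have a higher short-term rate of acute events. They would raise the comparator rate, pull the IRR down and could mask a risk. The effect should fade as the window lengthens.
- **Registered but absent people.** Someone who has moved away without formal de-registration produces no recorded events and is read as event-free. This person would lower the comparator rate and push the IRR up. In the concurrent cohort they are also unlikely to be censored by vaccination, while real comparators are (median follow-up under 2 months, 9.1.1), and they remain available for matching with replacement.

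The comparison with concurrent unvaccinated subjects serves primary objective 4. Active comparators do not share the gap because they are vaccinated, but that comparison is exploratory, limited to two-dose recipients and subject to the feasibility assessment in 9.7.3.4.

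**Working it through.** **1. The plan's own precision figure.** Section 9.5 gives a 75% probability that the upper 95% limit for GBS lies below 3.0 (5 million vaccinated, 2 per 100,000 person-years, 84 days, 3:1 person-time, true IRR 1).

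- Vaccinated events A = 5,000,000 × 84/365.25 × 2/100,000 = 23.0; comparator events B = 23.0/3 = 7.67.
- SE = √(1/23.0 + 1/7.67) = 0.417.
- P = Φ(ln 3/0.417 − 1.96) = 0.750.

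The figure reproduces. It describes random error only and assumes no selection bias.

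**2. Inpatients.** Let a share p of comparators be inpatients with R times the AESI rate of the others, averaged over the window. With no vaccine effect, IRR = 1/(1 + p(R − 1)). Both p and R are assumptions.

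| p | R | null IRR |
|---|---|---|
| 0.5% | 10 | 1/1.045 = 0.96 |
| 0.5% | 20 | 1/1.095 = 0.91 |
| 1% | 10 | 1/1.09 = 0.92 |
| 1% | 20 | 1/1.19 = 0.84 |

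**3. Absent people.** Let a share g of comparator person-time belong to people with no recordable events. Then IRR = 1/(1 − g): 1.01 at 1%, 1.05 at 5%, 1.11 at 10%. The values of g are assumptions.

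Head-count and person-time shares differ in the concurrent cohort. Matching is 1:1 but 9.5 expects person-time of 3:1, so the average comparator is followed about a third as long as the average vaccinee. If absent people were followed as long as vaccinees, their share of comparator person-time would be about three times their share of heads. Then 3% of heads gives 1/(1 − 0.09) = 1.10, and 5% gives 1/(1 − 0.15) = 1.18. This is an upper case and does not carry over to the historical cohort, where nobody is censored by COVID-19 vaccination.

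**4. Both together.** With absent share g and inpatient share p, IRR = 1/((1 − g − p) + pR).

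- g = 5%, p = 0.5%, R = 10: 1/0.995 = 1.01
- g = 10%, p = 0.5%, R = 10: 1/0.945 = 1.06
- g = 10%, p = 1%, R = 20: 1/1.09 = 0.92

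The net sign depends on values the protocol does not give.

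**5. Scale against random error.** Table 4 reports 3,938,490 + 517,015 + 609,842 + 336,889 + 154,858 = 5,557,094 matched vaccinees. Using 84 days each, the 3:1 ratio and the background rates in Table 5, as one simple pooled total:

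- VTE (100 per 100,000 person-years): about 1,278 and 426 events; limit factor exp(1.96 × √(1/1278 + 1/426)) = 1.12.
- Bell's palsy (38 per 100,000): about 486 and 162 events; limit factor 1.19.
- GBS (2 per 100,000): about 25.6 and 8.5 events; limit factor 2.17.

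Biases of the size in steps 2 and 3 could rival random error for the commoner AESIs, but would be small beside it for GBS.

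**The case against.** The protocol has several safeguards, and they narrow the concern.

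- **SCRI.** It uses vaccinees only, so comparator eligibility cannot bias it. Table 3 marks kidney injury, liver injury, myocardial infarction and ARDS as suitable. A reader might infer that short-window risks in general would be hidden. The document does not support that, because these four have a second estimate free of the problem. Sudden death, TTS and thrombocytopenia with bleeding do not.
- **AESI exclusions.** An inpatient already coded with the AESI in the look-back leaves that analysis, along with the matched partner. This argues against very large rate ratios. A reader could reach 0.67 from 1% inpatients at 50 times the rate (1/1.49), but nothing in the protocol points to that pairing. People admitted for another reason remain, and no look-back applies to sudden death.
- **Frailty matching.** Palliative care, metastatic cancer and nursing-home residence are among the indicators in Annex Table 2, so some dying patients are matched. This is not a test of being in hospital.
- **Propensity score.** Annex Table 3 lists hospitalisations, visits, prescriptions and testing, and 9.7.7 allows restriction to more similar subjects. A reader might infer that absent people will be paired by score with present non-users. That assumes score matching, whereas the abstract and 9.7.7 also allow stratification or weighting and 9.7.10.1 refers to weighting. Under any method, past use cannot tell a healthy non-user from someone who has left, nor identify who is in a bed that day.
- **Negative controls and disclosure.** Urinary infection and fracture over 12 days (9.7.10.1) may reveal bias but do not remove it, and opposite biases can offset there. Section 9.9.1 acknowledges healthy vaccinee bias without restricting eligibility.

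The practical objections also stand. Admission data are not uniform: HES covers only linked English practices (9.4.1), SIDIAP hospital linkage is arranged by project (9.4.3), and PHARMO hospital data lag by a year (9.4.5). A contact rule may select different people in 2017-2018 than in the pandemic, because 9.1.1 says care-seeking and access changed. The data listed for ARS Toscana in 9.4.4 do not include GP visits, so a contact would mean different things by source.

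**Conclusion.** The gap is real and lies in the protocol's own eligibility list. Section 9.2.1.1.3 leaves sampling and matching details to the SAP, but it states the inclusion criteria itself, and none concerns inpatient status or presence on the index date.

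Neither direction nor size can be claimed. The illustrative null IRRs (0.96 to 0.84 for inpatients, 1.05 to 1.11 for absent person-time) rest on assumed shares and rate ratios, hold the rate ratio constant over the window and precede propensity score adjustment. It would be wrong to read them as showing that the study will miss risks or produce false signals. They show that modest, unmeasured shares could move an estimate by as much as its confidence limit for the commoner AESIs. The consequence is greatest for outcomes with no SCRI, such as sudden death, TTS and thrombocytopenia with bleeding.

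**What to change.** 1. **Section 9.2.1.1.3.** Where admission data are available, including HES-linked CPRD at the final analysis, require both members of each vaccinated-concurrent and vaccinated-historical pair not to be in hospital on the index date. State by data source whether the rule is applied.
2. **Section 9.7.10.** Add a sensitivity analysis requiring at least one recorded contact (visit, dispensing, test or admission) in the prior 12 months for both members of each pair. Report it beside the cohort without the contact rule, and read it with caution for the historical comparison.

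**Cost.** The sample becomes slightly smaller and less general, because some genuine non-users of care are lost from both sides of the contact analysis. The admission filter cannot be applied uniformly. CPRD supplies 3,938,490 of 5,557,094 matched vaccinees (71%) and needs HES for it, so sources with and without the filter would have to be distinguished in any pooling. Table 2 places the end of data collection for the final report in late 2023, after this version, so both changes can still be specified in advance.
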